#### 5 STUDY ENROLLMENT AND WITHDRAWAL

The study target sample size is 220 English- and Spanish-speaking children with ASD. We anticipate a 4:1 ratio of boys to girls in the ASD group based on current statistics (CDC, 2014) and consistent with recruitment in our R34 study. Based on our results from our R34 SADE study, we anticipate that the ethnic and racial backgrounds of our sample will mirror the general population of CHLA patients. Specifically, we expect more than half of individuals to be of Hispanic/Latino origin with a preponderance of Caucasian children.

Based on our R34-funded pilot study, we plan to recruit children with ASD from CHLA Dental Clinic. Each week, study staff will review the electronic health records of the list of patients scheduled for a dental cleaning in the CHLA Dental Clinic. For those appearing to meet inclusion criteria for the study, study staff will contact the parents or guardians and invite participation in the study.

Based on our pilot study, we found that it may be difficult to recruit a sufficient number of children with a range of ASD severity. Therefore, for this study we plan to recruit children from multiple sites including CHLA (Dental Clinic, USC UCEDD, Boone Fetter Clinic, AltaMed), and the Los Angeles Unified School District. See Section 5.3 for greater detail about these sites.

# 5.1 Subject Inclusion Criteria

In order to be eligible for the proposed study, all individuals must meet all of the following criteria:

- Provide signed and dated informed consent (parent permission) and child assent (if appropriate) forms.
- Willing to comply with all study procedures and be available for the duration of the study.
- Male or female, aged 6 through 12 years.
- Have an accompanying parent or guardian who speaks English or Spanish.
- Live within local commuting distance of CHLA.
- Have experienced at least one prior dental cleaning.
- Diagnosed with Autism Spectrum Disorder, based on the Autism Diagnostic Observation Scale, 2nd ed (ADOS-2) as administered by a psychologist from our research team.
- Need an oral cleaning (defined as no oral cleaning within the previous four months).
  - Participants are eligible to be enrolled and complete study Visits 1 and 2 if they
    have had an oral cleaning within the previous four months. However, participants
    will not be eligible to complete Study Visit 3 until a minimum of four months has
    passed following their previous dental cleaning.

# 5.2 Subject Exclusion Criteria

An individual who meets any of the following criteria will be excluded from participation in this study:

- Cleft palate or other oral condition which makes dental care more difficult than usual practice.
- Prescription of anti-cholinergic drugs (which may alter EDA) (See Appendix M in MOP for a list of medications)
- Presence of orthodontia (braces).

- Significant motor impairment, such as cerebral palsy.
- Any known genetic, endocrine, or metabolic dysfunctions.
- Participation in the R34 SADE pilot study.
- Any medical condition such as significant cardiac problems that would place the individual at increased risk in the study.

# 5.3 Strategies for Recruitment and Retention

# Recruitment at each site

**CHILDREN'S HOSPITAL LOS ANGELES (CHLA).** CHLA will be our main recruitment site and is a nonprofit, academic, major pediatric medical center providing healthcare to children throughout Los Angeles and surrounding counties. Within CHLA, participants will be recruited through several sources:

CHLA Division of Dentistry and Orthodontics. The Division of Dentistry and Orthodontics, aligned with the USC School of Dentistry, provides routine and specialized dental care to approximately 3,500 children and adolescents each year, including more than 300 children with ASD. Participants with ASD will be recruited from lists of currently scheduled patients; recruitment flyers will be posted in the Dental Clinic and dentists will also be asked to distribute flyers to appropriate clients who have ASD. These flyers will contain contact information for the research staff, enabling parents to contact the research team if they are interested in participating in the study.

USC Center for Excellence in Developmental Disabilities at CHLA (UCEDD). The USC UCEDD, which is part of the CHLA Division of General Pediatrics, is one of more than 65 university centers in the U.S. focused on training, service, research, and technical assistance for people with disabilities and their families. Each year, the UCEDD provides diagnostic and intervention services to over 3,000 children with disabilities, including approximately 200 children with ASD. Recruitment flyers will be posted at the UCEDD and therapists will be asked to distribute flyers to clients who have ASD.

Boone Fetter Clinic. The Boone Fetter Clinic at CHLA offers comprehensive services for children thought to have autism, neurodevelopmental, or behavioral disorders, offering clinical diagnostic and assessment services and serving as a follow-up resource referral for children with ASD. Boone Fetter provides diagnostic services to approximately 120 children with ASD each year. Recruitment flyers will be posted at the Boone Fetter Clinic and therapists will be asked to distribute flyers to clients who have ASD.

AtlaMed General Pediatrics Service. AltaMed, designed to eliminate disparities in health care access and outcomes, provides quality health and human services to 16,000 underserved Southern California children. Conservatively, 200 of these children are diagnosed with ASD. [name], Director of AltaMed, will assign a pediatrician as a 5% in-kind contribution to this U01 study; this pediatrician will identify potential study participants and provide them with information about the study.

Participants from previous research studies. Participants will also be recruited from a list of children with ASD who have participated in previous research studies at CHLA who have consented to be approached about additional research opportunities. These include participants

from the Tummy Troubles Study (Grant # 1R21MH089465-01, PI: [name]). [name] (Co-I) has access to this database of approximately 200 previous participants in research at CHLA, including over 100 children with ASD. [name] will provide these potential study participants with information about the study.

LOS ANGELES UNIFIED SCHOOL DISTRICT (LAUSD). In order to ensure that children with a wide range of ASD severity are recruited and enrolled in this study, LAUSD will also be a source of participant recruitment. LAUSD is the second largest public school system in the United States, enrolling over 350,000 students in our targeted age range. Conservatively, we estimate that over 2,500 are diagnosed with ASD. These local schools also serve primarily low-income Latino children (70%), similar to the demographics at CHLA. Schools within local commuting distance of CHLA have been identified, and, with principal approval, recruitment flyers will be disseminated to children with ASD. After flyer dissemination, interested parents will be responsible for contacting the research team via provided contact information (phone or email) for further details of participation.

**OCCUPATIONAL THERAPY CLINICS**. In order to ensure we reach target enrollment, pediatric occupational therapy clinics will also be a source of participant recruitment. *Pediatric Therapy Network* serves over 2,500 children with special needs and provides over 100,000 hours of occupational therapy, physical therapy, and speech-language therapy each year as well as offering multiple small group programs (e.g., Early Intervention, social skills, augmentative and alternative communication, etc.). *Therapy West* has three facilities in the greater Los Angeles area to provide occupational therapy, physical therapy, and/or speech and language therapy, treating primarily children with developmental disabilities including Down Syndrome, Cerebral Palsy, and Autism Spectrum Disorders.

#### Retention

To aid in retention of study participants, a series of steps will be taken. Reminder phone calls, texts, and/or e-mails for meetings and dental visits will occur (based on stated parent preference). Additionally, the first meeting, consisting of the consent process and survey completion, will take place at the family home or CHLA, whichever is more convenient for the family. Utilizing these strategies in the R34 pilot study, we were able to retain 98% of our participants. However, since not all participants will be patients in the CHLA Dental Clinic, we expect there may be a larger loss. We have allowed for a loss of 10%, targeting a sample of 165 participants with complete data from a recruited sample of 220 children with ASD.

# Compensation

Families will not incur any out-of-pocket costs for participating in this study. Families' insurance will be billed for one of the two dental visits, and the other visit will be provided free of charge. If a participant does not have dental insurance, or if the insurance company denies reimbursement, both dental cleanings will be free of charge. Additionally, participants will be paid a stipend following each visit to compensate families for their time as for well as parking and transportation costs.

The amount and schedule of payments is as follows:

1. Consent and survey completion visit: \$40 following completion of questionnaires

- 2. Administration of ADOS-2 for ASD diagnosis confirmation and IQ test (WASI-II): \$40 following assessment plus \$10 parking/transportation
- 3. First Dental Cleaning Visit: \$40 plus \$10 parking/transportation
- 4. Second Dental Cleaning Visit: \$40 plus \$10 parking/transportation (provided only if the study's rideshare option is not used). For our final 25 participants, new CHLA procedures that are COVID-19 related are designed to protect the safety of the parent/legal guardian and participant. Round-trip rideshare will be available for these 25 participants.

Note: To protect the health and safety of patients and staff during the COVID-19 pandemic, CHLA implemented a new policy that requires participants to take the COVID-19 test 72 hours prior to a scheduled dental cleaning visit. This will be scheduled by CHLA at no cost to the participant. If the participant wishes, a round-trip rideshare (e.g. Lyft) will be available to the participant for this visit. In addition, the participants will be provided with a \$25 stipend for their time. This additional stipend will be provided at the patient's dental cleaning visit. This process will continue as long as COVID-19 testing prior to the dental visit is required by CHLA. The study team will follow the most current CHLA procedures and guidelines and as changes are made, we will abide by the most current CHLA procedures and guidelines. See MOP Appendix P Children's Hospital Los Angeles Pre-procedural COVID-19 Testing and Appendix Q: Children's Hospital Los Angeles COVID-19 Telephone Screening Procedures for additional details about the procedures.

Participants tested prior to the pandemic were able to receive a maximum of \$190. For the remaining participants affected by the CHLA policy during the COVID-19 pandemic, the participant will receive a maximum of \$215.

#### 5.4 Treatment Assignment Procedures

# 5.4.1 Randomization Procedures (if applicable)

Following confirmation of ASD diagnosis (administration of ADOS-2), participants will be randomly assigned to the order of treatment, receiving either the Regular Dental Environment (RDE) condition or Sensory Adapted Dental Environment (SADE) condition for their first cleaning. Because we anticipate different rates of participation between gender and age, randomization will be stratified by gender and age (6.0-9.5 years and 9.6-12.11 years) so there is a balance in order of treatment between boys and girls and younger and older children in each order of environment. Randomization will be performed by our PhD biostatistician following a blocked randomization schema for each of the gender-age stratum. We anticipate that the largest stratum will be younger boys (~56% of the sample), followed by older boys (24%), younger girls (15%), and older girls (6%), thus block sizes will vary so that the study team cannot anticipate what the first treatment for a participant will be.

# 5.4.2 Masking Procedures (if applicable)

For intra-oral photos and analysis of EDA recordings, coders will be blinded to condition (SADE vs. RDE). Due to the practicalities of this study and the need to modify dental environments for each patient, blinding of treatment condition for patients or dentists is not applicable.

# 5.5 Subject Withdrawal

Subjects may withdraw voluntarily from the study. The investigator may also terminate a subject's participation if the second scheduled dental cleaning cannot be completed within a maximum of 8 months following the first dental cleaning (see Section 7.5 for more details).

# 5.5.1 Reasons for Withdrawal

Subjects are free to withdraw from participation in the study at any time upon request.

An investigator may terminate a study subject's participation in the study if:

- Any clinical serious adverse event (SAE), laboratory abnormality, or other medical condition or situation occurs such that continued participation in the study would not be in the best interest of the subject.
- The subject meets an exclusion criterion (either newly developed or not previously recognized) that precludes further study participation.
- The subject cannot tolerate electrodes placed on fingertips.

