#### 6.2 Administration of Intervention

The private dental room for the SADE will be prepared by trained research team members. Following the set-up of the environment and electrode placement on the study participant's fingers, a three-minute baseline rest period will occur, followed by the dental cleaning led by the CHLA resident. In the RDE, the same research team members will video-record, place electrodes, and obtain EDA recordings, but none of the environmental adaptations will be made.

Each participant will receive a total of two dental cleanings approximately four-six months apart. In this crossover design, one cleaning will be in SADE and the other in the RDE. The duration of each dental cleaning session will be approximately 15-45 minutes.

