#### 7.2 Enrollment/Baseline

# **Enrollment Visit (Visit 1, Day 0)**

- Further explain study protocol and participant responsibilities in greater detail than that discussed on the screening for eligibility phone call. Answer any parent or child questions.
- Verify inclusion/exclusion criteria.
- Obtain and document consent from parent on study consent (parental permission) form. Explain and obtain signature from parents on study HIPAA form.
- Explain and provide parents with California Bill of Rights.
- Obtain and document child assent from child subject on study assent form (if child is available and able to complete/understand form).

• Parental completion of the Parent Bilingual Questionnaire to assess the child and parent's bilingual preference (see Appendix N in MOP).

- Use the Decision Tree for Accepting Child's Data as a guideline to determine if the child is able to give assent based on the parent report (see Appendix O in MOP).
- Parental completion of study questionnaires to obtain demographic information, dental history, anxiety, and sensory over-responsivity. (Complete list of measures to be completed are listed in the Schedule of Events in Appendix A; see CRFs 5-10, 28: Child & Family Information (Demographics), CASI-Anx, SSP-2, SensOR, CFSS-DS, VABS-II Expressive Communication Domain, Dental History Form, Dental Care in Children Questionnaire)
- Child completion of study questionnaires (if able) to obtain information about child perception of dental anxiety. (Complete list of measures to be completed are listed in the Schedule of Events in Appendix A; see CRFs 11-12: CFSS-DS, MCDASf)
- Parents are shown and instructed in the use of the specialized study social story for going to the dentist and participating in the SADE study. Parents are informed that the social story will be mailed to them with instructions two weeks prior to the child participant's first (and second) dental cleaning.
- Parents and children are shown the EDA electrodes and allowed to play with them.

*Note:* This visit (Visit 1) will take place at the participant's home, or if the family prefers, at CHLA, prior to the Autism Diagnostic Confirmation Visit (Visit 2).

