#### 7.3 Intermediate Visits

# ASD Diagnosis Confirmation and IQ Testing (Visit 2, Day 1 to 270)

- At the enrollment visit (Visit 1), parents are informed that their child will need to have the ADOS-2 and WASI-II administered at the CHLA UCEDD (parents will also be informed of this during the phone screening prior to this visit). Parent contact information will be provided to [name] and her staff at the CHLA UCEDD for scheduling. A phone screening process will occur during the scheduling call to determine the appropriate ADOS module to be utilized during the ADOS-2 administration. Confirmation of ASD diagnosis through ADOS-2 administration is required to continue with visits for oral cleaning. If child does not meet the ASD criteria based on the ADOS-2, services or treatment at the dental clinic will continue as before but the child will not continue as a research participant nor participate in the study's subsequent visits. If a study participant has previously had the ADOS-2 administered at the CHLA UCEDD, we will accept the ASD confirmation and study results from that previous assessment.
- Child completion of study Assent (if child was not present at Visit 1 and is able to complete/understand form)
- ASD diagnostic confirmation (Autism Diagnostic Observation Schedule 2) and cognitive screen (Wechsler Abbreviated Screening of Intelligence II) administered by [name] or a psychology member of her team.

- All parents/guardians will receive written feedback (by mail) from [name] or a member of her team regarding the general results of the autism and cognitive assessments (see Appendix I in MOP)
- Following completion of Visit 2, randomization into study condition (RDE vs. SADE) for the first dental visit (Visit 3) will occur (see Section 5.4.1 for randomization details).
  - \*\*This behavioral assessment (ADOS-II) must be completed and confirm ASD diagnosis prior to the continuation of study activities and administration of intervention.

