### 7.5 Withdrawal Visit

There will not be a withdrawal visit and no evaluations are specifically required for the final visit as the final visit is the second dental cleaning visit (Visit 4 above).

We will make every attempt to ensure that each child gets two dental cleanings, one in each condition (SADE and RDE). Missed appointments will be rescheduled, as many times as necessary up to eight months following the child's first dental cleaning (with participants receiving priority scheduling), extra reminders made, and compensation provided to cover transportation costs and time. If a child does not complete his/her second cleaning within eight

months of his/her first, we will assume that he/she has voluntarily withdrawn and will inform parents that their child is no longer eligible to obtain the second dental cleaning, nor is part of the study anymore. Parents will also be reminded that there will be no penalty or impact on CHLA quality of care as a result of withdrawing or dropping out of the study.

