# 12.4 Final Analysis Plan

Descriptive statistics will be performed for all variables of interest to describe the participant population at baseline, including attrition rate and missing data, to compare those randomized to SADE first vs. those randomized to RDE first. We anticipate a low attrition rate (~10%) and will impute missing data for intent-to-treat analyses using Markov Chain Monte Carlo (MCMC)

imputation with multiple values imputer for each missing value averaged for an estimation for analyses. Bivariate associations between outcomes (physiological anxiety and children's negative behavioral responses), environment (SADE or RDE), and covariates (age, gender, order of visit, autism severity, IQ, and sensory sensitivity) will be described. The primary objective of determining difference between dental environments will be tested using intent-to-treat models examining the within-subject factor of dental environment (SADE vs RDE) using repeated measures ANCOVA for each outcome. *A priori* covariates include age (continuous), randomized order of visit, gender, and temperature. Other participant characteristics that are unbalanced between order of visits will be included as covariates *ad hoc*.

The secondary objective of examining the mediating effect of physiologic response on behavioral outcomes will be tested by first examining the bivariate relationships between EDA and behavioral outcomes, and then adding EDA estimates (SCL and NS-SCR) to models of dental environment difference on behavioral outcomes, and examining the change in the within group coefficients. A change in coefficient >15% will be considered evidence of mediation. While we have several outcomes, we specify only one mediator, thus we will apply a rational approach to examination of multiple outcomes, and will assess the fidelity of our study by estimating effect sizes (Cohen's d) of the dental environment before and after the mediation factors are assessed to confirm that statistical results were supported by clinical relevance of findings. If physiological anxiety does mediate the environment's effect on negative behavioral responses, we anticipate that the anticipated effect of environment will be eliminated once we add in EDA to the models specified in Hypothesis 2. Analyses will be performed using SPSS (v.22); a priori two-sided  $\square = 0.05$ .

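### Electrode intolerance can end a child's whole participation after randomisation, which gives up behaviour, pain, sensory, cost and plaque outcomes that need no electrodes

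*Combined protocol and SAP*

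**What the plan says.** Section 5.5.1 opens its list with "An investigator may terminate a study subject's participation in the study if", and the last item is "The subject cannot tolerate electrodes placed on fingertips". What ends is participation in the study, not only EDA recording.

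Three passages fix the timing:

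- Section 7.3, Visit 2: "Following completion of Visit 2, randomization into study condition (RDE vs. SADE) for the first dental visit (Visit 3) will occur".
- Section 6.2: "Following the set-up of the environment and electrode placement on the study participant's fingers, a three-minute baseline rest period will occur". Section 6.3 also puts electrode application first in the sequence of the cleaning visit.
- Section 7.2, before randomisation: "Parents and children are shown the EDA electrodes and allowed to play with them". This is familiarisation. Sections 5.1 and 5.2 do not make electrode tolerance an eligibility criterion.

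Sections 3.2.2 and 8.1 describe the outcomes that do not use electrodes: the Children's Dental Behavior Rating Scale (CDBRS) from video, the dentist's Frankl and Anxiety and Cooperation ratings, the child's pain (FPS-R) and sensory discomfort (DSSS) reports, cost items from video and notes, and plaque from intra-oral photographs.

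Section 12.4 plans intent-to-treat models with MCMC imputation and does not mention this group. Section 5.5.2 gives replacement rules for voluntary withdrawal and for certain safety events, but not for electrode terminations. Section 7.5 provides no withdrawal visit. No section says that the other outcomes are still collected once a child is ended on this ground.

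**The concern.** A measurement problem with one instrument can become the loss of every outcome for that child. Because electrodes go on first, a child ended at placement at Visit 3 may have no outcome in either period. A child ended at Visit 4 keeps one period but loses the within-child pair on which the comparison rests.

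The loss is unlikely to be random. The introduction reports tactile over-responsivity in 61% of children with ASD, Section 2.2.1 names discomfort with the electrodes as a risk, and Hypothesis 4 expects a larger SADE benefit in sensory over-responsive children. Intolerance also shows itself inside the assigned room, so it could differ by environment. Section 5.5.1 does not define when electrodes are not tolerated, and staff in the room know the condition. At stake are the size and make-up of the sample for secondary objectives (a), (c) and (d).

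**Working it through.** **1. The plan's own figure.** Section 12.2 gives 165 children with repeated measures for a within-child d = 0.22 at 80% power. The paired formula at two-sided 0.05 gives n = ((1.960 + 0.842)/0.22)² = 162.2, so 163; the t-based value is 164.1, so 165. The figure reproduces.

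**2. Rate.** None is given. I assume q = 2%, 5% and 10% of 220, that is 4.4, 11 and 22 children. The pilot cannot exclude this range. Even if none of its 22 children with ASD had been intolerant (the documents do not say so), the one-sided 95% upper bound would be 1 − 0.05^(1/22) = 12.7%.

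**3. Power for an electrode-free outcome.** Two-sided 0.05, starting from 165, with the electrode losses assumed to come on top of the planned loss:

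| q | children left | power, d = 0.22 | power, d = 0.23 |
|---|---|---|---|
| 0 | 165 | 80.2% | 83.6% |
| 2% | 160.6 | 79.1% | 82.6% |
| 5% | 154 | 77.4% | 81.0% |
| 10% | 143 | 74.3% | 78.0% |

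The value 0.23 is the top of the pilot range for distress behaviour (0.11-0.23, Section 12.2). The primary EDA analysis is not part of this cost: a child who cannot wear electrodes has no EDA for that visit under either rule.

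**4. Sensory moderator.** Suppose first that the children lost are exactly the top q of a normally distributed moderator. With c the (1 − q) quantile and λ = φ(c)/(1 − q), the retained variance is V = 1 − cλ − λ². At q = 2%, c = 2.0537 and λ = 0.0494, so V = 0.896. At 5% and 10%, V = 0.810 and 0.712.

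If intolerance correlates with the moderator at ρ (bivariate normal), the retained variance is 1 − ρ²(1 − V). The number of analysed children needed for the same power rises by its reciprocal:

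| q | ρ = 0.3 | ρ = 0.5 | ρ = 1 |
|---|---|---|---|
| 2% | 1.01 | 1.03 | 1.12 |
| 5% | 1.02 | 1.05 | 1.24 |
| 10% | 1.03 | 1.08 | 1.40 |

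For example, at q = 10% and ρ = 0.5: 1 − 0.25 × (1 − 0.712) = 0.928, and 1/0.928 = 1.08. No section gives a value for ρ. The factors count analysed children; the children lost come on top.

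**5. Shift in the average effect.** If the effect in the children lost is k times that in the others, the tolerant-only effect divided by the effect in all children is 1/((1 − q) + qk). At q = 10% this is 1/1.1 = 0.91 for k = 2 and 1/0.9 = 1.11 for k = 0. At q = 2% it is 0.98 and 1.02. Both q and k are assumed.

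**6. What new wording can still reach.** Note-3 to Visit 4 in Section 7.3 says that all participants had completed Visits 1-3 by March 2020 and 25 still awaited the second cleaning. The assumed rates give 25 × 0.02 = 0.5 to 25 × 0.10 = 2.5 children. These children have already been through one cleaning visit, so the true number is probably at the low end.

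**The case against.** The strongest reply is that few children are likely to be affected. The pilot retained 98% of participants and reported no adverse reactions to the electrodes, and children handle the electrodes at Visit 1 and receive a social story showing their application. This stands as a reason to expect a low rate. It is limited by the pilot's 22 children with ASD and by this trial's aim of a wider range of severity.

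The clause is also permissive and has a rationale. The investigator can keep the child, and EDA is both the primary outcome and the mediator, so a child without it gives no observed data for Hypotheses 1 and 3. Both points are true. But discretion without a criterion leaves retention to staff who know the condition, and neither point justifies giving up the other outcomes.

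Four stronger readings are tempting, and the documents do not support them:

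- *The rule removes the most sensory-sensitive children.* Nothing links electrode intolerance to the sensory scale. The link is plausible, but it is an inference.
- *Every secondary outcome is biased.* The contrast is within-child, so a child lost at Visit 3 mainly narrows the population. Bias is possible, and loss that differs by environment is undocumented.
- *The rule contradicts Section 7.5.* The phrase "We will make every attempt to ensure that each child gets two dental cleanings" there concerns rescheduling of missed appointments within eight months. It does not override other withdrawal grounds.
- *The rule contradicts intent-to-treat.* Section 12.4 excludes no terminated child from the analysis. The fair criticism is narrower: obtainable data are lost and then imputed.

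**Conclusion.** The point holds in a limited form. The rule can end all data collection for a child after randomisation because of an instrument that only EDA needs. The resulting loss is plausibly related to a hypothesised moderator and possibly to the environment. Imputation does not recover outcomes that could have been observed, and it rests on a missing-at-random assumption that is doubtful here.

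The size is uncertain and probably modest. Under the assumed 2-10% loss, power for an electrode-free outcome at d = 0.22 falls by about 1 to 6 percentage points from 80.2%. The moderator test needs about 3-8% more analysed children at ρ = 0.5. A reader might take the 12-40% at ρ = 1 as the expected cost, but it requires intolerance and the moderator to coincide exactly, which nothing in the plan shows. The moderator models are also labelled exploratory in Section 12.4. The change should be made, although most of its remaining value lies in analysis and reporting.

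**What to change.** - In Section 5.5.1, separate missing EDA from ended participation. Treat electrode intolerance as missing EDA for that visit, not as a ground to end study data collection.
- Record the reason, visit and environment each time.
- Keep collecting the electrode-free outcomes if the cleaning goes ahead. Whether it goes ahead stays with the clinician and parent; nothing here bears on that decision.
- Reconcile Sections 5.5.1, 5.5.2 and 12.4, so that they state whether such a child is replaced and how the child enters the intent-to-treat analysis.
- For the whole trial, report EDA missingness and electrode terminations by environment and visit, and include whatever electrode-free data exist from terminated children in the intent-to-treat analysis.

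The cost is protocol wording, a short recording item and one table. New wording can affect only the 25 outstanding second cleanings; the reporting and analysis items cover everyone randomised. The downside is that some children will contribute secondary outcomes but no EDA, so the numbers analysed will differ between outcomes and should be shown.
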